2.4.5.4 Analyses of vital sign variables

The summary statistics (including number, mean, median, Q1, Q3, SD, minimum and maximum) of all vital signs variables (values and changes from baseline) will be calculated for each visit or study assessment (baseline, each post-baseline time point, and last on-treatment) by treatment group. For all parameters, mean changes from baseline with corresponding standard error will be plotted over time in each treatment group.

The incidence of PCSAs at any time during the TEAE period will be summarized by treatment group irrespective of the baseline level and/or according to the following baseline status categories:

- Normal/missing
- Abnormal according to PCSA criterion or criteria

Listings will be provided with flags indicating the PCSA values.

2.4.5.5 Analyses of electrocardiogram variables

The summary statistics (including number, mean, median, Q1, Q3, SD, minimum and maximum) of all ECG variables (central laboratory values and changes from baseline) will be calculated for each visit or study assessment (baseline, each post-baseline time point, and last on-treatment) by treatment group. For all parameters, mean changes from baseline with corresponding standard error will be plotted over time in each treatment group.

The incidence of PCSAs at any time during the TEAE period will be summarized by treatment group irrespective of the baseline level and/or according to the following baseline status categories:

- Normal/missing
- Abnormal according to PCSA criterion or criteria

Listings will be provided with flags indicating the PCSA values.

2.4.6 Analyses of pharmacokinetic and pharmacodynamic variables

2.4.6.1 Analyses of serum concentrations

Serum concentrations will be analyzed in the PK population. Concentrations of SAR440340 will be summarized in SAR440340-treated patients. Concentrations of dupilumab will be summarized in dupilumab-treated patients.

Arithmetic and geometric means, SD, standard error of the mean (SEM), coefficient of variation (CV), minimum, median and maximum per sampling time will be provided. If date and/or time of the drug injection and/or sampling is missing then the concentration will not be taken into account. Concentrations below the lower limit of quantification (LLOQ) will be set to zero for pre-dose samples (Week 0). Other concentrations below LLOQ will be replaced by LLOQ/2. Values will be expressed in the tables with no more than three significant figures.

2.4.6.2 Pharmacodynamics/genomics analyses

PD biomarkers will be analyzed in the safety population. Baseline values will be the last value collected prior to the first IMP.

For all parameters, absolute change from baseline and percent change from baseline will be summarized descriptively (number, arithmetic and geometric means, SD, SEM, CV, median, minimum, and maximum) by treatment group and time point. Values reported as below the LLOQ will be imputed as LLOQ/2.

Summary plots (mean +/- standard error of the mean) of levels, absolute changes from baseline and percent changes from baseline by visit and plot of median percent change (with interquartile range) from baseline by visit will be provided for each biomarker by treatment group.

Exploratory analysis of DNA/RNA will be addressed in a separate document.

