#### **4.4 COADMINISTRATION OF SAR440340 WITH DUPILUMAB**

Increasingly it is appreciated that severe asthma is a complex and heterogeneous condition. While OCS are often required in this condition due to their broad anti-inflammatory effects, the side effects of these agents are unacceptable for long term use. Targeted mAb approaches which block single pathways may not be sufficient to treat the most severe patients and hence it is suggested that combination of mAbs which target separate yet complementary pathways and which are safe

and efficacious may be a successful and safe approach to treat the most severe, complex asthma phenotypes. The mechanism of action of SAR440340 and dupilumab as well as preclinical data in a mouse model of chronic HDM allergic inflammation suggest that the coadministration of SAR440340 with dupilumab may have additive anti-inflammatory effects compared to either SAR440340 or dupilumab alone, due to both distinct and overlapping effects of each mAb.

Humanized mice expressing human IL33, IL4, and IL4R $\alpha$  (Il33hu/hu, Il4hu/hu, Il4rahu/hu mice) exposed to HDM extract thrice-weekly for 19 weeks were treated twice-weekly from Week 12 to Week 19 with SAR440340, dupilumab, coadministration of SAR440340 and dupilumab, or an isotype control antibody. Gross lung pathology type 1 and/or type 2 immune response markers were assessed. The combination of SAR440340 and dupilumab showed improved efficacy compared to either treatment alone at preventing HDM-induced increases in lung weight, at reducing HDM-induced lung inflammation, with statistical significance for lung hIL4, IL-6, tumor necrosis factor (TNF $\alpha$ ), growth related oncogene (GRO $\alpha$ ), monocyte chemoattractant protein-1 (MCP-1) and myeloperoxidase (MPO) relative to control IgG4P, and at reducing serum IgE and serum amyloid A protein (SAA). In addition, a recent publication has demonstrated in two well established murine models of asthma that dual inhibition of both IL33 and IL13 was more efficacious than inhibiting each cytokine alone in reducing airway eosinophilia, levels of IL5 in bronchoalveolar lavage as well as ILC2 cells in the lung (20).

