#### **11.4.4.3 Pharmacodynamics**

The values to be used as baseline will be those collected on Day 1 (predose assessments). If any of the scheduled assessments on Day 1 are technically disqualified (eg, insufficient sample) and the parameters are measured at any of the screening visits, then values determined at screening can be used as the baseline.

For all parameters, raw data, absolute changes from baseline and percent changes from baseline will be summarized by treatment group and time point using descriptive statistics.

Summary plots (mean±standard error of the mean) on raw data, absolute changes from baseline, and percent changes from baseline will be provided by treatment group.

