1.3 DETERMINATION OF SAMPLE SIZE

Data from a previous 12-week study of dupilumab with similar design, population, and background treatment (ACT11457) showed an 87% relative reduction in the rate of LOAC (44% in placebo group versus 6% in dupilumab group).

The sample size calculations are based on the primary endpoint, incidence of LOAC with the following assumptions:

- Incidence rate of 40% in the placebo group
- A 26% absolute rate reduction (to 14%) in the SAR440340 group
- A 2-sided χ^2 test at 5% significance level with 80% power

[figure not shown]
Based on the above assumptions, and allowing for approximately 15% dropout rate, 60 patients per treatment group are needed.

Calculations were made using nQuery Advisor 7.0.

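### SAP 2.4.6.2 asks for geometric means of absolute and percent change for every biomarker; these cannot be computed once any patient's change is zero or negative (minor, descriptive tables only)

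*SAP*

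**What the plan says.** SAP 2.4.6.2 covers the pharmacodynamic markers listed in SAP 2.1.7: blood eosinophils and neutrophils, FeNO, eotaxin-3, PARC, total IL33, sST2, calcitonin, total IgE and periostin. Its table specification, which applies to every one of them, is that "absolute change from baseline and percent change from baseline will be summarized descriptively (number, arithmetic and geometric means, SD, SEM, CV, median". The list ends with the range.

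The same section adds: "Values reported as below the LLOQ will be imputed as LLOQ/2". It also plans plots of mean level, mean absolute change and mean percent change by visit, and a "plot of median percent change (with interquartile range) from baseline by visit will be provided for each biomarker by treatment group".

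The section does not define a geometric mean for a change score, gives no rule for values at or below zero, and does not say whether the CV is arithmetic or geometric. SAP 2.5.7, on statistical technical issues, is marked not applicable.

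Two other places matter for comparison:
- SAP 2.4.6.1 uses nearly the same list for serum drug concentrations: "Arithmetic and geometric means, SD, standard error of the mean (SEM), coefficient of variation (CV), minimum, median and maximum per sampling time".
- Protocol 11.4.4.3 says: "For all parameters, raw data, absolute changes from baseline and percent changes from baseline will be summarized by treatment group and time point". It names neither a geometric mean nor a CV. SAP 1.6 declares no departure from the protocol.

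**The concern.** Geometric mean and CV suit positive, skewed quantities such as concentrations, which is how SAP 2.4.6.1 uses them. SAP 2.4.6.2 applies the same list to differences from baseline, which can take either sign. The LLOQ/2 rule keeps levels above zero but does nothing for changes. A programmer therefore has to invent a rule that the SAP does not supply, and one easy choice (log the values and let the non-positive ones go missing) puts a wrong-direction figure in the study tables.

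Biomarkers of the IL33 and IL4/IL13 pathways are among the other objectives in Protocol 5.3. Falls are plausible: the mouse data in Protocol 4.4 report lower serum IgE with the combination, and total IgE is one of the listed markers.

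There is a second gap. The quantity for which these statistics are valid, the measured level, is plotted but missing from the table list in SAP 2.4.6.2. Eosinophils and neutrophils are tabulated elsewhere, as hematology variables (SAP 2.1.4.3 and 2.4.5.3). The other markers are not.

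**Working it through.** The plan states no figure on this point, so there is nothing to reproduce. The check is of definitions, followed by an illustration.

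**Definitions.** For values x, geometric mean = exp(mean(log x)), which requires every x > 0. Arithmetic CV = 100 × SD / mean, which is undefined only if the mean is exactly zero and is negative when the mean is negative. Percent change = (ratio − 1) × 100, where ratio = post-baseline / baseline, so percent change is above zero only if the ratio exceeds 1.

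**Five-patient example (invented values).** Percent changes −60, −50, −40, −30, +10.
- Arithmetic mean = −170 / 5 = −34; median = −40.
- Squared deviations from −34: 676 + 256 + 36 + 16 + 1936 = 2920. SD = √(2920 / 4) = 27.0. CV = 100 × 27.0 / (−34) = −79%.
- Geometric mean of the five changes: undefined, because four are negative. Over the one positive value only: +10.
- Ratios 0.4, 0.5, 0.6, 0.7, 1.1 have product 0.0924. Geometric mean ratio = 0.0924^(1/5) = 0.621, or −37.9%.

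**Arm-sized illustration.** The 60 patients per arm come from SAP 1.3. Everything else is assumed, not taken from the documents: log-normal ratio to baseline, geometric mean ratio 0.5 to 1.2, log-SD 0.3 to 0.5, 4000 simulated arms per scenario. All columns after the log-SD describe percent change. The positives-only value is averaged over arms in which at least one patient rose.

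| True ratio | Log-SD | Share of patients rising | Geometric mean, positives only | Arithmetic mean | Median | CV, 5th to 95th percentile | From geometric mean ratio |
|---|---|---|---|---|---|---|---|
| 0.5 | 0.3 | 1% | +10.9% | −47.8% | −50.0% | −42% to −26% | −50.0% |
| 0.5 | 0.5 | 8% | +18.9% | −43.4% | −49.9% | −103% to −46% | −49.9% |
| 0.8 | 0.3 | 23% | +12.6% | −16.3% | −19.9% | −266% to −102% | −19.9% |
| 0.8 | 0.5 | 33% | +25.9% | −9.3% | −19.7% | −2412% to +1741% | −19.8% |
| 1.0 | 0.3 | 50% | +18.4% | +4.7% | +0.3% | −2429% to +3450% | +0.2% |
| 1.0 | 0.5 | 50% | +33.7% | +13.4% | +0.4% | +234% to +1693% | +0.3% |
| 1.2 | 0.3 | 73% | +27.2% | +25.5% | +20.2% | +116% to +204% | +20.1% |
| 1.2 | 0.5 | 64% | +42.8% | +36.2% | +20.6% | +147% to +293% | +20.5% |

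In every scenario all simulated arms held at least one change at or below zero. Direct arithmetic agrees. The chance that all 60 patients rise is 0.5^60, about 9 × 10⁻¹⁹, with no true change. Even in the most favourable row it is 0.73^60, about 6 × 10⁻⁹.

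The geometric mean ratio uses every patient and returns the assumed effect. The arithmetic mean percent change lies above the assumed effect in every row because ratios are skewed. The median does not share that shift.

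**The case against.** The strongest reply is that little is lost. The same sentence of the SAP also tabulates arithmetic mean, SD, SEM, median, minimum and maximum, and the section adds mean plots and a median percent-change plot. A reader might infer that markers lowered by the drugs get no valid summary, or only one in the wrong direction. The documents do not support that: direction is shown several times over, and the median answers the skew in the arithmetic mean.

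A reader might also infer that the tables will show a rise in every arm. That requires a positives-only programming rule, which the SAP does not state. The alternative is an empty cell, which misleads nobody. The positives-only column above is therefore the result of one possible workaround, under assumed effects and spreads.

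Nor is the CV undefined in the way the geometric mean is. An arithmetic CV exists unless the mean change is exactly zero. It is merely negative or unstable, and so hard to interpret.

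Finally, it is not true that the SAP tabulates no levels at all. SAP 2.4.5.3 summarizes hematology values and changes by visit, which covers eosinophils and neutrophils at the hematology visits. For the other markers, the protocol's raw-data commitment has not been withdrawn, so the gap is an omission from one list.

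All of this stands and limits the reach of the point. None of it makes the geometric mean of a change score computable.

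**Conclusion.** The defect is real and minor. SAP 2.4.6.2 specifies a statistic that practically no arm will be able to produce as defined. The exception would be a marker that rises in every patient of an arm. The CV beside it is negative or unstable for change scores, and its type is not named. For all markers except eosinophils and neutrophils, the protocol's raw-data summary has no matching table in the SAP.

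That the geometric mean fails rests on its definition alone. The sizes rest on the assumed log-normal ratios and spreads: if non-positive changes are dropped, a true halving appears as +11% to +19%, and a true 20% fall as +13% to +26%.

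The reach is the geometric-mean and CV cells of descriptive biomarker outputs under the other objectives. The LOAC and FEV1 analyses are not affected, and no test or decision rule in the plan uses these cells.

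**What to change.** In SAP 2.4.6.2:
- Delete geometric mean and CV for absolute and percent change. Keep arithmetic mean, SD, median and range for these.
- Tabulate observed levels by arm and visit, as Protocol 11.4.4.3 intends, with the geometric mean and a CV whose type is stated.
- Add the ratio to baseline, analysed on the log scale: geometric mean ratio with 95% CI by arm and visit, back-transformed as (ratio − 1) × 100. With LLOQ/2 applied it is defined for every patient who has both values. State a rule for any level recorded as exactly zero rather than as below the LLOQ.

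The first two changes cure the defect. The third is an addition that gives a log-scale summary of change using every patient. The cost is SAP wording and table shells, with no new data and no change to trial conduct.

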2.4.7 Analyses of immunogenicity data

2.4.7.1 Analysis of ADA bioanalytical data

Analyses described in this section will be performed separately for ADA against SAR440340 and ADA against dupilumab in all treatment groups unless otherwise specified.

ADA response categories and titer categories are defined as follows:

- **Pre-existing immunoreactivity:** defined as either an ADA positive response in the assay at baseline with all post first dose ADA results negative, OR a positive response at baseline with all post first dose ADA responses less than 4-fold (for anti-dupilumab) or 9-fold (for anti-SAR440340), over baseline titer levels.
- **Treatment-emergent response:** defined as a positive response in the ADA assay post first dose when baseline results are negative or missing.
- **Treatment-boosted response:** defined as a positive response in the ADA assay post first dose that is greater than or equal to 4-fold (for anti-dupilumab) or 9-fold (for anti-SAR440340) over baseline titer levels, when baseline results are positive.

A treatment-emergent response is further classified as persistent, indeterminate or transient:

- **Persistent response:** treatment-emergent ADA response detected at 2 or more consecutive ADA positive sampling time points, separated by at least 16-week period (based on nominal sampling time), for both anti-dupilumab and anti-SAR440340, with no ADA negative samples in between.
- **Indeterminate response:** treatment-emergent response when only the last collected sample is positive.
- **Transient response:** a treatment-emergent response that is not persistent or indeterminate.
- **ADA positive patients:** patients with treatment-emergent or treatment-boosted response.
- **ADA negative patients:** patients with pre-existing immunoreactivity or negative in the ADA assay at all time points.

Titer values (Titer value category)

- Low (Titer < 1000)
- Moderate (1,000 ≤ Titer ≤ 10,000)
- High (Titer > 10,000)

The following summaries will be provided based on ADA population:

Baseline summary:

- Number (%) of patients with a positive response in the ADA assay at baseline
 - Summary statistics (including number, median, Q1, Q3, minimum, and maximum) of titer for patients with a positive response
- Number (%) of patients with a negative response in the ADA assay at baseline

Post-baseline summary:

- Number (%) of patients with treatment-emergent ADA response
 - Number (%) with persistent response
 - Number (%) with indeterminate response
 - Number (%) with transient response
- Number (%) of patient with treatment-boosted ADA response
- Number (%) of ADA positive patients
- Number (%) of ADA negative patients
- Number (%) of patients with pre-existing immunoreactivity

Listing of all ADA peak titer levels will be provided for treatment emergent and treatment-boosted ADA response patients.

2.4.7.2 Association of immunogenicity with exposure, safety and efficacy

The potential association between key ADA variables (ADA positive, persistent ADA and titer) and exposure, safety and efficacy will be explored.

Possible associations between ADA and PK (exposure)

Associations between key ADA variables and systemic exposure to study drug will be explored by treatment group. The following summaries will be provided:

- Descriptive summary of functional SAR440340 concentrations by anti-SAR440340 antibody patient classification in SAR440340-treated patients at each visit
- Descriptive summary of functional dupilumab concentrations by anti-dupilumab antibody patient classification in dupilumab-treated patients at each visit

In addition, plots of drug concentration may be provided for analyzing the potential impact of ADA on PK.

Possible association between ADA and clinical efficacy

Associations between the key ADA variables and key efficacy endpoints will be explored by treatment group. Plots of efficacy variables may be provided for potential impact of ADA on efficacy.

Possible association between ADA and clinical safety

Association of safety versus key ADA variables will be explored by treatment group. The safety assessment may focus on the following events:

- Injection site reaction (serious or severe and lasting 24 hours or longer)
- Hypersensitivity reactions
- Anaphylactic reactions

2.5 DATA HANDLING CONVENTIONS

2.5.1 General conventions

Demographic formulas

- Age at onset of asthma (years) is calculated as:
$$\text{Year of diagnosis of asthma} - \text{Year of birth}$$
- Time since first diagnosis of asthma (years) is calculated as:
$$(\text{Year of randomization} - \text{Year of first diagnosis of asthma}) + (\text{month of randomization} - \text{month of first diagnosis of asthma})/12$$
- Time since cessation of smoking (years) is calculated as:
$$(\text{Year of randomization} - \text{Year of cessation}) + (\text{month of randomization} - \text{month of cessation})/12$$
- Time since last asthma exacerbation (months) is calculated as:
$$(\text{Year of randomization} - \text{Year of last asthma exacerbation}) \times 12 + (\text{month of randomization} - \text{month of last asthma exacerbation})$$
- BMI is calculated as:
$$\text{Weight in kg} / (\text{height}^2 \text{ in meters})$$
- Smoking quantity (pack-year) is calculated as following:
$$\text{Number of pack-year} = (\text{packs smoked per day}) \times (\text{years as a smoker})$$

Renal function formulas

Creatinine clearance (CrCl) value will be derived using the equation of Cockcroft and Gault:

$$\text{CLcr (ml/min)} = (140 - \text{age}) \times \text{weight (kg)} \times (1 - 0.15 \times \text{sex (0-M, 1-F)}) / (0.814 \times \text{creatinine } (\mu\text{mol/l}))$$

CLcr will be calculated using the last weight measurement on or before the visit of the creatinine measurement and age at the lab sampling date. Here age is calculated as following:

$$\text{Integer part of (Lab sampling date - Date of screening visit) / 365.25} \\ + \text{Age at screening visit}$$

2.5.2 Data handling conventions for other efficacy variables

Calculation of salbutamol/albuterol or levosalbutamol/levalbuterol inhalations/day

The number of salbutamol/albuterol or levosalbutamol/levalbuterol inhalations per day is the sum of number of inhalations recorded in one diary day including the evening diary and the following day's morning diary.

Periodical average of daily efficacy endpoints at designated study days

For the daily efficacy endpoints, the time period used to calculate the periodical average at each designated study day is summarized in [Table 6](#). First IMP administration is used as the reference day (Day 1).

Table 6 - Periodical average of daily efficacy assessment

Time point	Morning PEF, asthma symptom score, number of awakenings	Evening PEF, asthma symptom score	Number of inhalations/day of salbutamol/albuterol or levosalbutamol/levalbuterol
Day 8	2-8	1-7	Diary Day 1-7
Day 15	9-15	8-14	Diary Day 8-14
Day 22	16-22	15-21	Diary Day 15-21
Day 29	23-29	22-28	Diary Day 22-28
Day 36	30-36	29-35	Diary Day 29-35
Day 43	37-43	36-42	Diary Day 36-42
Day 50	44-50	43-49	Diary Day 43-49
Day 57	51-57	50-56	Diary Day 50-56
Day 64	58-64	57-63	Diary Day 57-63
Day 71	65-71	64-70	Diary Day 64-70
Day 78	72-78	71-77	Diary Day 71-77
Day 85	79 - (Day of EOT)	78 - (Day before EOT)	Diary Day 78 - (Day before EOT)

Note: A diary day is defined as the period beginning with an Evening diary, and ending with the following day's Morning Diary. For example, diary day 14 includes the evening diary on day 14 and the morning diary on day 15.

2.5.3 Missing data

For categorical variables, patients with missing data are not included in calculations of percentages unless otherwise specified. When relevant, the number of patients with missing data is presented.

Handling of computation of treatment duration if investigational medicinal product end of treatment date is missing

For the calculation of the treatment duration, the date of the last dose of IMP is equal to the date of last administration reported on the end-of-treatment case report form page. If this date is missing, the exposure duration should be left as missing.

The last dose intake should be clearly identified in the case report form and should not be approximated by the last returned package date.

Handling of medication missing/partial dates

No imputation of medication start/end dates or times will be performed. If a medication date or time is missing or partially missing and it cannot be determined whether it was taken prior or concomitantly, it will be considered a prior and concomitant medication.

Handling of adverse events with missing or partial date/time of onset

Missing or partial adverse event onset dates and times will be imputed so that if the partial adverse event onset date/time information does not indicate that the adverse event started prior to treatment or after the treatment-emergent adverse event period, the adverse event will be classified as treatment-emergent. No imputation of adverse event end dates/times will be performed. These data imputations are for categorization purpose only and will not be used in listings. No imputation is planned for date/time of adverse event resolution.

Handling of adverse events when date and time of first investigational medicinal product administration is missing

When the date and time of the first IMP administration is missing, all adverse events that occurred on or after the day of randomization should be considered as treatment-emergent adverse events. The exposure duration should be kept as missing.

The last dose intake should be clearly identified in the case report form and should not be approximated by the last returned package date.

Handling of missing assessment of relationship of adverse events to investigational medicinal product

If the assessment of the relationship to IMP is missing, then the relationship to IMP has to be assumed and the adverse event considered as such in the frequency tables of possibly related adverse events, but no imputation should be done at the data level.

Handling of missing severity of adverse events

If the severity is missing for one of the treatment-emergent occurrences of an adverse event, the maximal severity on the remaining occurrences will be considered. If the severity is missing for all the occurrences, a “missing” category will be added in the summary table.

Handling of potentially clinically significant abnormalities

If a patient has a missing baseline he will be grouped in the category “normal/missing at baseline.”

For PCSAs with 2 conditions, one based on a change from baseline value or a normal range and the other on a threshold value, with the first condition being missing, the PCSA will be based only on the second condition.

For a PCSA defined on a threshold and/or a normal range, this PCSA will be derived using this threshold if the normal range is missing; eg, for eosinophils the PCSA is > 0.5 GIGA/L or $> \text{ULN}$ if $\text{ULN} \geq 0.5$ GIGA/L. When ULN is missing, the value 0.5 should be used.

Measurements flagged as invalid by the laboratory will not be summarized or taken into account in the computation of PCSA values.

